7.2.1 Enrollment and Baseline (Day 1)

Participants will be approached within 2-3 days of beginning residential treatment based on initial screening from EMR and enrolled into the study if they consent.

The following **standard of care data** will be collected from the EMR for research purposes:

- Demographic information (age, gender, race, contact information)
- Detailed medical history
- Physical examination
- Admission diagnoses

- Results from standard laboratory safety tests performed on admission (complete blood count, comprehensive metabolic panel)
- Current medication usage (concomitant medications)
- Results of urine pregnancy test at admission (if applicable)

The following **research-only activities** will be performed prior to randomization:

- A psychiatric assessment will be conducted:
 - o M.I.N.I. 7.0.2
 - o Form 90-DI
 - o HAM-D
 - o STAI-Y1
 - o C-SSRS
- Body weight will be measured
- 12-lead EKG will be performed
- Collection of stress response, sleep, and activity measurements will be initiated via actigraphy wristband (a "wearable" wristband).

Any participant that reports recent suicidal ideation or behavior on the screening C-SSRS will be referred for further immediate evaluation by a clinician. Clinical judgement and additional consult with the Caron Medical Director, study PI, and/or study staff will be used to further clarify if the subject is eligible to continue in the study.

Participant will receive the actigraphy wristband from a study coordinator. The study coordinator will instruct the subject on use of the actigraph.

Randomization: After obtaining written consent, subjects who fulfill study criteria will be randomized to either the liraglutide or placebo treatment arm of the study using an equal allocation ratio (1:1) permuted-block randomization.

The following **research-only activities** will occur after randomization and will serve as baseline values to compare with values obtained after study drug dosing:

- Cue-elicited drug craving will be evaluated using VAS.
- Neurophysiology measurements using fNIRS and VAS.
- Collection of ambient drug craving, mood, and sleep data will be initiated with EMA.
- Monitoring of body weight and cardiorespiratory function.
- Aes and concomitant medications will be documented.

Collection of blood pressure, heart rate and respiratory rate data will be initiated with cardiorespiratory testing performed by study staff.

Collection of ambient drug craving, mood, and sleep data will be initiated with EMA. Participant will use the smartphone containing EMA surveys they received prior to randomization. A study coordinator will instruct the subject on use of the phone.

Cue-elicited drug craving will be evaluated by a study coordinator using VAS.

7.2.2 Study Drug Treatment, Dose 1 (Days 2-7)

During this time, the following research-only activities will occur:

 Blood samples will be collected on Day 2, prior to study drug administration, for monitoring of glycemic control. This will include measurements of HbA1c and fructosamine. Approximately 2 teaspoons of blood will be collected.

- During Days 2-7, liraglutide/placebo control will be administered daily at 0.6 mg before breakfast.
- Aes and concomitant medications will be documented.
- Ambient drug craving, mood, and sleep data will be collected on Days 2, 3, 6, and 7 via EMA assessment.
- Stress response, sleep, and activity measurements will be collected daily via actigraphy wristband.
- Body weight data will be collected daily.
- On Day 2, cardiorespiratory function will be measured as described in Section 7.2.

Subjects will be taught administration of liraglutide by a Caron nurse on Day 2 during the first injection of the lowest dose. Repeated instruction on liraglutide administration may be provided on subsequent drug administration days if requested by the participant until they are comfortable with the procedure.

7.2.3 Study Drug Treatment, Dose 2 (Days 8-13)

During this time, the following research-only activities will occur:

- During Days 8-13, 1.2 mg of liraglutide/placebo control will be administered daily at a specified time (prior to breakfast).
- Aes and concomitant medications will be documented.
- Ambient drug craving, mood, and sleep data will be collected on Days 8, 9, 12, and 13 via EMA assessment.
- Stress response, sleep, and activity measurements will be collected daily via actigraphy wristband.
- Body weight data will be collected daily.
- On Day 8, cardiorespiratory function will be measured as described in Section 7.2.

7.2.4 Study Drug Treatment, Dose 3 (Days 14-18)

During this time, the following **research-only activities** will occur:

- During Days 14-19, 1.8 mg of liraglutide/placebo control will be administered daily at a specified time (prior to breakfast).
- Aes and concomitant medications will be documented.
- Ambient drug craving, mood, and sleep data will be collected on Days 14, 15, and 18 via EMA assessment.
- Stress response, sleep, and activity measurements will be collected daily via actigraphy wristband.
- Body weight data will be collected daily.
- On Day 14, cardiorespiratory function will be measured as described in Section 7.2.

7.2.5 Study Test Day – (Day 19)

The following **research-only** measures, all completed on Day 1, will be repeated on Day 19, regardless of intervention length (i.e., 3-dose and 5-dose interventions). Day 19 will serve as the final dose (1.8 mg) day for participants in the 3-dose intervention. For participants in the 5-dose intervention, Day 19 will be the final day at the 1.8 mg dose before moving on to the 2.4 mg dose on Day 20.

- Cardiorespiratory function will be assessed via measurement of blood pressure, heart rate, and respiratory rate as described in Section 7.2.
- Blood samples will be collected for safety laboratory tests (CBC, CMP) and for monitoring of glycemic control. Approximately 4 teaspoons of blood will be collected.
- Body weight data will be collected.

- Cue-elicited drug craving will be evaluated using VAS.
- Neurophysiology measurements will be evaluated using fNIRS during: (1) Visual cue reactivity and (2) BART.
- Collection of ambient drug craving, mood, and sleep data by EMA.
- Stress response, sleep, and activity measurements will be collected via actigraphy wristband.
- C-SSRS
- Urine pregnancy test (if applicable)
- Aes and concomitant medications will be documented.

7.2.6 Days 20-21

For 3-dose intervention participants: Rebound Evaluation Period

During this time the following **research-only** measures will occur:

- Collection of ambient drug craving, mood, and sleep data by EMA through Day 21, then discontinued.
- Stress response, sleep, and activity measurements will be collected via actigraphy wristband through Day 21, then discontinued.
- Aes and concomitant medications will be documented through Day 21.
- Body weight data will be collected through Day 21.
- On Day 21, cardiorespiratory function will be measured as described in Section 7.2.

The smartphone and actigraphy wristband will be collected by a study coordinator on Day 22.

For 5-dose intervention participants: Study Drug Treatment, Dose 4

During this time, the following research-only activities will occur:

- During Days 20-21, 2.4 mg of liraglutide/placebo control will be administered daily at a specified time (prior to breakfast).
- Aes and concomitant medications will be documented.
- Ambient drug craving, mood, and sleep data will be collected on Days 20-21 via EMA assessment.
- Stress response, sleep, and activity measurements will be collected daily via actigraphy wristband.
- Body weight data will be collected daily.

On Day 20, cardiorespiratory function will be measured as described in Section 7.2.

7.2.7 Study Drug Treatment, Dose 4 (Days 22-25) [5-dose intervention only]

During this time, the following research-only activities will occur:

- During Days 22-25, 2.4 mg of liraglutide/placebo control will be administered daily at a specified time (prior to breakfast).
- Aes and concomitant medications will be documented.
- Ambient drug craving, mood, and sleep data will be collected on Days 24 and 25 via EMA assessment.
- Stress response, sleep, and activity measurements will be collected daily via actigraphy wristband.
- Body weight data will be collected daily.

7.2.8 Study Drug Treatment, Dose 5 (Days 26-30) [5-dose intervention only]

During this time, the following research-only activities will occur:

- During Days 26-31, 3.0 mg of liraglutide/placebo control will be administered daily at a specified time (prior to breakfast).
- o Aes and concomitant medications will be documented.

- Ambient drug craving, mood, and sleep data will be collected on Days 26, 27, and 30 via EMA assessment.
- Stress response, sleep, and activity measurements will be collected daily via actigraphy wristband.
- Body weight data will be collected daily.
- On Day 26, cardiorespiratory function will be measured as described in Section 7.2.

7.2.9 Study Test Day – (Day 31) [5-dose intervention only]

The following **research-only** measures, all completed on Day 1 and Day 19, will be repeated on Day 31.

- Cardiorespiratory function will be assessed via measurement of blood pressure, heart rate, and respiratory rate as described in Section 7.2.
- Blood samples will be collected for safety laboratory tests (CBC, CMP) and for monitoring of glycemic control. Approximately 4 teaspoons of blood will be collected.
- Body weight data will be collected.
- Cue-elicited drug craving will be evaluated using VAS.
- Neurophysiology measurements will be evaluated using fNIRS during: (1) Visual cue reactivity and (2) BART.
- Collection of ambient drug craving, mood, and sleep data by EMA.
- Stress response, sleep, and activity measurements will be collected via actigraphy wristband.
- C-SSRS
- Urine pregnancy test (if applicable)
- Aes and concomitant medications will be documented.

7.2.10 Rebound Evaluation Period, (Days 32-33) [5-dose intervention only]

During this time the following **research-only** measures will occur:

- Collection of ambient drug craving, mood, and sleep data by EMA through Day 33, then discontinued.
- Stress response, sleep, and activity measurements will be collected via actigraphy wristband through Day 33, then discontinued.
- Aes and concomitant medications will be documented through Day 33.
- Body weight data will be collected through Day 33.
- On Day 33, cardiorespiratory function will be measured as described in Section 7.2.

The smartphone and actigraphy wristband will be collected by a study coordinator on Day 34.

7.2.11 End of Study telephone call (Day 49 [Day 61 for 5-dose intervention])

All participants will have an End of Study telephone call. This will occur 30 days (+/- 5 days) from the discontinuation of medication. Patients will be asked to self-report their body weight at the time of the call.

Schedule of Study Activities: 3-Dose Study Drug Intervention

	Enrollment/ Baseline		Intervention		Test Day (Final dose)	Off Drug	Rebound Evaluation	Equipment Return	End of Study Telephone Call**
	Day 1	Days 2-7	Days 8-13	Days 14-18	Day 19	Day 20	Day 21	Day 22	30 days +/- 5 days end of medication
Study Drug/Placebo Dose		0.6 mg	1.2 mg	1.8 mg	1.8 mg	-		-	
Informed consent	Х								
Data collected from Electronic Medical Record ¹	х								
M.I.N.I International Neuropsychiatric Interview (M.I.N.I. 7.0.2)	Х								
Form 90-Drug Inventory (Form 90-DI)	Х								
Hamilton Depression scale (HAM-D)	Х								
State-Trait Anxiety Inventory (STAI-Y1)	х								
Columbia Suicide Severity Rating Scale (C-SSRS)	Х				Х				
Body weight	Х	х	x	X	Х	х	х		X
12-lead electrocardiogram (EKG)	Х								
Pregnancy test ²	Х				Х				
Cardiorespiratory function assessment ³	Х	Х	Х	Х	Х		Х		
Blood samples for fructosamine and A1c		X ⁴			Х				
Cue-elicited drug craving ⁵	X*				х				

	Enrollment/ Baseline		Intervention		Test Day (Final dose)	Off Drug	Rebound Evaluation	Equipment Return	End of Study Telephone Call**
	Day 1	Days 2-7	Days 8-13	Days 14-18	Day 19	Day 20	Day 21	Day 22	30 days +/- 5 days end of medication
Study Drug/Placebo Dose		0.6 mg	1.2 mg	1.8 mg	1.8 mg	•		-	
Neurophysiology measurements ⁶	X*				Х				
Safety labs (CBC and CMP)					Х				
Ambient drug craving, mood, and sleep ⁷	X*	Х	Х	х	Х	Х	Х		
Actigraphy wristband ("wearable" wristband) ⁸	Х	х	х	Х	Х	Х	Х		
Concomitant medications	Х*	Х	Х	х	х	Х	х		
Adverse events	Χ*	Х	Х	Х	Х	Х	х		Х
Return of actigraphy wristband and smartphone								Х	

^{*}Performed AFTER randomization has occurred.

^{**}ALL participants, unless they withdraw consent, will have an end of study telephone call.

¹Demographics, medical history, admission diagnoses, and current medication usage.

²If female with childbearing potential, will collect results from test at admission as data for Day 1, with research-only pregnancy tests at Day 19.

³Performed on Day 1, Day 2, Day 8, Day 14, Day 19, and Day 21.

⁴Performed on Day 2 only

⁵Using Visual Analog Scales (VAS).

⁶Using fNIRS, VAS, and BART.

⁷Collection of ambient drug craving, mood, and sleep data will be initiated with Ecological Momentary Assessment (EMA). Collected on Days 1-3, 6-9, 12-15, and 18-21.

⁸Stress response, sleep, and activity measurements.

Schedule of Study Activities: 5-Dose Study Drug Intervention

	Enrollment/ Baseline		Intervention						Off Drug	Rebound Evaluation	Equipment Return	End of Study Telephone Call**
	Day 1	Days 2-7	Days 8-13	Days 14-18	Day 19	Days 20-25	Days 26-30	Day 31	Day 32	Day 33	Day 34	30 days +/- 5 days end of medication
Study Drug/Placebo Dose		0.6 mg	1.2 mg	1.8 mg	1.8 mg	2.4 mg	3.0 mg	3.0 mg	-		-	
Informed consent	Х											
Data collected from Electronic Medical Record ¹	Х											
M.I.N.I International Neuropsychiatric Interview (M.I.N.I. 7.0.2)	Х											
Form 90-Drug Inventory (Form 90-DI)	Х											
Hamilton Depression scale (HAM-D)	х											
State-Trait Anxiety Inventory (STAI-Y1)	х											
Columbia Suicide Severity Rating Scale (C-SSRS)	Х				Х			Х				
Body weight	х	Х	х	х	х	х	х	х	х	х		x
12-lead electrocardiogram (EKG)	х											
Pregnancy test ²	Х				х			Х				
Cardiorespiratory function assessment ³	Х	Х	х	Х	х	х	х	х		х		
Blood samples for fructosamine and A1c		X ⁴			Х			Х				
Cue-elicited drug craving ⁵	X*				х			Х				

	Enrollment/ Baseline			Interv	ention			Test Day (Final dose)	Off Drug	Rebound Evaluation	Equipment Return	End of Study Telephone Call**
	Day 1	Days 2-7	Days 8-13	Days 14-18	Day 19	Days 20-25	Days 26-30	Day 31	Day 32	Day 33	Day 34	30 days +/- 5 days end of medication
Study Drug/Placebo Dose		0.6 mg	1.2 mg	1.8 mg	1.8 mg	2.4 mg	3.0 mg	3.0 mg	-		-	
Neurophysiology measurements ⁶	X*				х			Х				
Safety labs (CBC and CMP)					х			Х				
Ambient drug craving, mood, and sleep ⁷	X*	Х	Х	Х	х	Х	Х	Х	х	Х		
Actigraphy wristband ("wearable" wristband) ⁸	х	х	х	Х	Х	Х	х	Х	х	Х		
Concomitant medications	X*	Х	Х	Х	Х	Х	Х	х	Х	Х		
Adverse events	X*	Х	Х	Х	Х	Х	Х	Х	Х	Х		Х
Return of actigraphy wristband and smartphone											Х	

^{*}Performed AFTER randomization has occurred.

^{**}ALL participants, unless they withdraw consent, will have an end of study telephone call.

¹Demographics, medical history, admission diagnoses, and current medication usage.

²If female with childbearing potential, will collect results from test at admission as data for Day 1, with research-only pregnancy tests at Day 19 and Day 31.

³Performed on Day 1, Day 2, Day 8, Day 14, Day 19, Day 20, Day 26, Day 31, and Day 33.

⁴Performed on Day 2 only

⁵Using Visual Analog Scales (VAS).

⁶Using fNIRS, VAS, and BART.

⁷Collection of ambient drug craving, mood, and sleep data will be initiated with Ecological Momentary Assessment (EMA). Collected on Days 1-3, 6-9, 12-15, 18-21, 24-27, and 30-33.

⁸Stress response, sleep, and activity measurements.

7.3 Duration of Participation

The total duration of study participation for each subject will be approximately 49 days (3-dose intervention) or 61 days (5-dose intervention).

7.4 Test Article(s) (Study Drug(s) and/or Study Device(s))

7.4.1 Description

Liraglutide (Saxenda®, Novo Nordisk) is a glucagon-like peptide-1 (GLP-1) receptor agonist approved by the FDA for the treatment of T2DM (1.8 mg/day) and obesity (3.0 mg/day) and has been deemed safe for use in populations with a history of substance use disorder (American Association of Clinical Endocrinologists, 2016; see also Saxenda package insert, Plainsboro, NJ: Novo Nordisk A/S; 2015).

Liraglutide 6 mg/ml (Novo Nordisk), will be provided as a solution in a pre-filled, multi-dose pen that delivers doses of 0.6 mg, 1.2 mg, 1.8 mg, 2.4 mg, or 3 mg of liraglutide as a subcutaneous injection.

Liraglutide and placebo will be delivered as a solution (liquid) in identical multidose pens. In order to use Saxenda® as a blinded comparator in the clinical trial, the presentation has been modified from the Marketed product. For Saxenda® (Comparator) the primary packaging materials are identical to what is approved in the Marketing authorization, except that the cartridge for the comparator is produced with an army green closure cap. The closure cap in the currently marketed Saxenda® product is a light blue cap. The cap is not in contact with the product and has no impact on the stability of the comparator. For Saxenda® (Comparator) the pen is identical to what is approved in the Marketing Authorization, except for the color of the cartridge holder and the pushbutton, where the Marketed version is purple and the clinical comparator is light brown. The pen is not in contact with the product and its color has no impact on the stability of the comparator.

New, unused liraglutide/vehicle pens will be stored according to the information stated on the trial product label. Pens will be disposed of after 30 days of initial use.

7.4.2 Treatment Regimen

The recommended maximum dosage is 3 mg/day, administered any time of day. This choice in dosage is based on the current FDA-approved dosing regimen for liraglutide to help patients manage craving in obesity. The initial dose will start at 0.6 mg/day for the first 6 days, then titrate by 0.6 mg every 6 days — to reduce the likelihood of adverse gastrointestinal symptoms — until 1.8 mg/day is reached for the 3-dose intervention and 3 mg/day is reached for the 5-dose intervention. Participants will be taught self-administration by study/nursing staff. All self-administrations will occur via blinded, multi-dose subcutaneous injection pens, and will be observed by nursing staff at CaronTC.

Participants will receive medications daily at a specified time (prior to breakfast) throughout the study. Participants will be taught to inject the solutions subcutaneously in the abdomen, thigh, or upper arm, and will administer daily injections under the supervision of a study nurse or staff member. Participants will be taught by study staff nurses to attach the needle, check the drug/vehicle flow, select the dose, inject the dose, remove the needle, and dispose of the needle. Participants will always use a new needle for each dose administration in the study. Dosages will be chosen based on current titration level in the study.

There is no provision to provide study treatment after the study.

7.4.3 Method for Assigning Subject to Treatment Groups

Participants will receive either liraglutide or placebo in a two-arm parallel group study. Interventions will be randomized in a 1:1 ratio using permuted-block randomization algorithm. The randomization will be performed using a random number generator via the PLAN procedure within SAS software, version 9.4 (SAS Institute Inc., Cary, NC). Personnel in the Department of Public Health Sciences (PHS) will use the PLAN procedure within SAS software to generate a randomization list using variable-size, random permuted blocks to ensure that the number of participants in each arm is balanced after each set of B randomized participants, where B is the block size. Personnel in PHS will choose the block sizes without revealing it to any of the investigators or study personnel who will be collecting and reviewing outcomes data. The randomization sequence will be uploaded to a secure REDCap database. Synergy Pharmacy will be given access to this REDCap database to provide the blinded, randomized labeling prior to shipping the study drugs to the CaronTC

7.4.4 Subject Compliance Monitoring

Nursing staff will chart administration of study drug into the patient's Caron EMR and study personnel will monitor and document the completion of all study procedures. Compliance is also being assessed through the wearables discussed above (Section 7.2) by a temperature sensor.

7.4.5 Blinding of the Test Article

The study drugs will be blinded to participants and investigators (double blind) through the distribution of identical injection pens. Injection pens will be ordered from Novo Nordisk and received in boxes by Synergy Pharmacy, an off-site pharmacy that works with the CaronTC. Each study drug pack will be sent to Synergy Pharmacy in a box containing a de-identified label for blinding purposes. Each box will have a specific Dispensing Unit Number (DUN). A total list of the DUNs (Total DUN list; TDL) will be supplied by Novo Nordisk indicating "liraglutide" or "placebo" for each DUNS number.

Unblinded personnel at Synergy Pharmacy will be available to handle the lists that reveal if the blinded product contains liraglutide or placebo. The laboratory staff analyzing the blood samples (as opposed to study coordinators) will be unaware of the condition and the treatment of the participants for whom they will conduct the assays as the samples will be identified only with a study number. The results of the laboratory measurements will not be shared with the treating physicians, and will not impact patient care except in an emergent situation.

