3.2 Exclusion Criteria

Patients will be excluded from study entry if any of the following exclusion criteria exist at screening:

- 1. Age < 18 or > 75 years
- 2. Women who are pregnant, planning pregnancy, breastfeeding, or unwilling to use adequate contraceptive measures
- 3. History of angioedema, serious hypersensitivity reaction, or anaphylactic reaction to liraglutide or another glucagon-like peptide-1 receptor (GLP1R) agonist
- 4. Personal or family history of medullary thyroid carcinoma (MTC) or patients with multiple endocrine neoplasia syndrome type 2 (MEN 2) or thyroid nodule
- 5. Type I diabetes or history of diabetic ketoacidosis
- 6. Type II diabetes mellitus
- 7. Hypoglycemia on intake visit (blood glucose < 70 mg/dL)
- 8. End-stated renal failure on dialysis **or** glomerular filtration rate (GFR) <30mL/min per 1.73 square meters **or** previous renal transplant
- 9. Severe hepatic impairment (AST or ALT levels > 3 times upper limit of normal range) or previous liver transplant
- 10. Current or past diagnosis of pancreatitis, gastroparesis, or other severe gastrointestinal disease
- 11. Current or past diagnosis of gallbladder disease or gallstones
- 12. Serious cardiovascular disease within the past 6 months (e.g. uncontrolled hypertension, heart failure, significant cardiac arrhythmias, myocardial infarction, presence of angina pectoris, symptomatic coronary artery disease, deep vein thrombosis, pulmonary embolism, second- or third-degree heart block, mitral valve or aortic stenosis, hypertrophic cardiomyopathy, stroke)

- 13. Severe co-occurring psychiatric disorder (e.g., bipolar disorder, psychotic disorder, schizophrenia) that would, in the opinion of the Principle Investigator or study physician, interfere with participating in the study, such as if the patient needs a higher or different level of care and is going to be transferred out of Caron.
- 14. Suicidal ideation within the past 1 month, or history of suicide attempts within the past 1 year, unless participation is cleared by clinician assessment and/or judgement.
- 15. Treatment with any investigational drug in the one-month preceding the study
- 16. Previous randomization for participation in this trial
- 17. Abnormal physical exam findings, vital signs (blood pressure, heart rate, respiratory rate, body temperature), EKG measurements, and safety lab values that are deemed clinically significant by study physician

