12.0 Sharing Results with Subjects

Any clinically relevant study results (including, but not limited to, EKG and blood tests) will be shared with subjects and their treating physicians. No other study results of an individual subject's result will be shared with subjects or any treating physician.

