18.3 Causality and Severity Assessments

The investigator will promptly review documented adverse events and abnormal test findings to determine 1) if the abnormal test finding should be classified as an adverse event; 2) if there is a reasonable possibility that the adverse event was caused by the study drug(s) or device(s); and 3) if the adverse event meets the criteria for a serious adverse event.

If the investigator's final determination of causality is "unknown and of questionable relationship to the study drug(s) or device(s)", the adverse event will be classified as associated with the use of the study drug(s) or device(s) for reporting purposes. If the investigator's final determination of causality is "unknown but not related to the study drug(s) or device(s)", this determination and the rationale for the determination will be documented in the respective subject's case history.

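### Sections 7.4.5 and 12.0 give opposite instructions on whether the treating physician learns of a laboratory result that is clinically relevant but not an emergency

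*Combined protocol and SAP*

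**What the plan says.** Section 7.4.5 ends its account of the blind with a rule on results: "The results of the laboratory measurements will not be shared with the treating physicians, and will not impact patient care except in an emergent situation". The sentence before it concerns laboratory staff who assay coded study samples. Neither sentence separates research assays from safety tests.

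Section 12.0, the section on returning results, says: "Any clinically relevant study results (including, but not limited to, EKG and blood tests) will be shared with subjects and their treating physicians". It then closes the door on all other individual results, for participants and treating physicians alike.

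The blood tests at issue are these. Section 7.2.2 has a pre-dose Day 2 draw for HbA1c and fructosamine. Section 7.2.5 says of Day 19: "Blood samples will be collected for safety laboratory tests (CBC, CMP) and for monitoring of glycemic control". Section 7.2.9 repeats this for Day 31 in the 5-dose intervention. The admission CBC and metabolic panel are standard of care, taken from the medical record (7.2.1), so Day 19 and Day 31 carry the only CBC/CMP panels scheduled on study drug.

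Neither section refers to the other.

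**The concern.** The two sections sort results by different tests. In 7.4.5 the dividing line is emergency; in 12.0 it is clinical relevance. Many results that matter to a patient's care are not emergencies, and for those the site holds two contrary written instructions.

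At stake is what the physician responsible for the patient in residential care knows and may act on. Followed to the letter, 7.4.5 keeps a relevant safety result from that physician and adds that it is not to influence care. Timing sharpens this a little. Day 19 is the last dosing day for a 3-dose participant, and Day 31 for a 5-dose participant. A result from that day's panel therefore leaves little or no dosing to stop, and follow-up care is its main remaining use.

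**Working it through.** No formula decides this point. The check compares the two rules case by case. The exception in 7.4.5 can be read two ways: as covering both clauses of the sentence (sharing and patient care), or only the second (patient care). An emergent result is taken to be clinically relevant as well.

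| Type of result | 7.4.5, exception covers both clauses | 7.4.5, exception covers care only | 12.0 | Consistent? |
|---|---|---|---|---|
| Not clinically relevant | Withhold | Withhold | Withhold | Yes |
| Clinically relevant, not emergent | Withhold; no effect on care | Withhold; no effect on care | Share | No, on either reading |
| Emergent | Share; may affect care | Withhold; may affect care | Share | Only on the first reading |

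1. The middle row is a direct conflict however the exception is read. The bottom row conflicts only if the exception attaches to patient care alone.
2. No other section sets precedence. Sections 18.2, 18.3 and 19.1.2 deal with recording, causality and AE assessment; 3.3.1 and 18.7 with removal; 18.6 with emergency unblinding. None directs a non-emergent result to the treating physician.
3. A concrete case. Exclusion 9 in Section 3.2 reads: "Severe hepatic impairment (AST or ALT levels > 3 times upper limit of normal range) or previous liver transplant". Suppose a symptom-free participant crosses that threshold on the Day 19 or Day 31 CMP. The protocol itself calls this level severe, so it is hard to class as irrelevant. Without symptoms it need not be an emergency. Section 12.0 sends it to the treating physician; 7.4.5 does not.
4. What the conflict leaves alone. Section 7.4.5 restricts sharing with treating physicians and does not mention participants, so the promise in 12.0 to inform the participant stands. Under 18.3, "The investigator will promptly review documented adverse events and abnormal test findings to determine" whether they are adverse events, drug-related or serious. Under 19.1.2, the PI makes AE assessments together with a physician team member or the medical monitor. Under 3.3.1 and 18.7, a newly developed exclusion condition leads to removal.
5. Scale of the panels involved. Section 8.2 gives 50 randomized and 20% attrition. If all attrition falls before Day 19, then 50 × (1 − 0.20) = 40 Day 19 panels. With E participants extending to Day 31, the total is 40 + E. E is not given and lies between 0 and 40, so the range is 40 to 80. The value 80 needs all 40 to extend, which 7.1 does not expect; replacement of withdrawn participants (3.3.2, 3.3.3) could add some. These are panels to which both rules apply, not conflicting results. The documents give no rate of clinically relevant, non-emergent findings, so the number of actual conflicts cannot be worked out.

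**The case against.** The strongest reply is that 12.0 is the section devoted to sharing results while 7.4.5 is a paragraph on blinding. On that view 7.4.5 states the default, 12.0 the exception, and all that is missing is a cross-reference. This is a workable reading and may be what was meant. It is not what the text says: 7.4.5 names its own exception, emergency, and gives no cue that a second one exists elsewhere.

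A second reply is that 7.4.5 covers only the research assays. Its wording carries no such limit, and the Day 19 and Day 31 draws combine safety and glycemic tests. Nor would the narrower scope remove the conflict, because 12.0 makes no exception for HbA1c or fructosamine. Section 7.2.2 says: "Blood samples will be collected on Day 2, prior to study drug administration, for monitoring of glycemic control". An HbA1c from that draw pointing to unrecognised diabetes (exclusion 6, "Type II diabetes mellitus") would still meet contrary rules. That condition would predate treatment, so the removal rule for conditions that develop during treatment does not clearly reach it. The example serves only to test the narrower reading.

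A third reply is that other safeguards cover the gap. Much of this stands. Abnormal findings believed to be drug-associated are followed until they resolve or stabilise (18.2), and some physicians at the treatment center are on the study team (4.2.1), so a result may reach the right person anyway. The protocol does not rely on that overlap.

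A reader might infer that the plan hides safety results from participants, or leaves people on study drug despite abnormal tests. The documents support neither, for the reasons in step 4 of the working. A reader might also infer that CBC/CMP values could never hint at allocation, since the treatment lists sit with unblinded pharmacy staff and unblinding has its own route in 18.6. Those provisions protect the codes; they do not establish that about the values. The point does not need it, because 12.0 already accepts sharing relevant results.

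**Conclusion.** The point holds in a narrow form. For a clinically relevant, non-emergent laboratory result, 7.4.5 and 12.0 are contradictory, and no text resolves them. If the emergency exception covers patient care only, the contradiction extends to emergent results too; the wording does not settle this. The defect is an internal inconsistency limited to what reaches the treating physician and whether it may affect care. It should be corrected because it concerns safety communication and costs almost nothing to repair.

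Its size cannot be stated as a number of patients. The 40 to 80 CBC/CMP panels show how widely the two rules apply, and should not be read as a count of affected participants. Endpoints, power and type I error are not involved. The liver-enzyme example assumes that the result would be judged relevant but not emergent; the protocol defines neither term. Confidence is high for the mismatch in wording and lower for how often it would matter in practice.

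**What to change.** Amend the last sentence of 7.4.5 so that its exception clearly governs both clauses and has two limbs. For example: laboratory results stay withheld from treating physicians and do not influence care unless the situation is emergent or the result is clinically relevant under Section 12.0. Add that passing on a result does not release the treatment code, and that unblinding remains under 18.6.

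The cost is one clause and a cross-reference, with no new tests, visits or unblinding.

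A helpful option is a sentence naming who reads the Day 19 and Day 31 CBC/CMP for clinical relevance, such as a study physician or the medical monitor. Two further changes are not needed to resolve the conflict: restricting the withholding to HbA1c and fructosamine, and making the step to 2.4 mg wait for a laboratory review.
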